#### **Anti-HSV medications**

**Efficacy.** Antiviral medication can suppress both symptomatic and asymptomatic reactivation of HSV-2. Acyclovir 400 mg twice a day is the most widely studied and clinically utilized regimen, and the newer antiviral regimens have not been shown to be superior. As shown in the figure below, twice daily acyclovir reduces the frequency of recurrences 80% compared to placebo, a slightly higher reduction than can be achieved with once daily regimens of valacyclovir. Furthermore, acyclovir 400 mg po bid has been shown to reduce viral shedding from 9.9% of the days to 0.5% of days in immunocompetent women . Acyclovir reduces viral shedding during clinical reactivation and subclinical episodes by comparable amounts (95% and 94% respectively). While a once daily regimen might be associated with higher compliance in terms of proportion of doses taken, the critical factor in the suppression of recurrences is the time above average in-vitro IC50 as shown below (Glaxo SmithKline, unpublished data). Thus the duration of time without adequate antiviral coverage is likely to be longer with a missed daily dose than a missed bid dose.

**Safety.** Acyclovir has been administered on a daily basis for up to 10 years without significant adverse effects. In terms of safety and tolerability, few if any antimicrobials rival acyclovir's record. Acyclovir has a safety profile that compares favorably with many over-the-counter medications. In fact, Burroughs Wellcome had petitioned the FDA to allow over-the-counter marketing of acyclovir for therapy of recurrent genital herpes. No safety concerns about this drug emerged at that time, based on analyses of adverse event reporting from clinical trials and of monitoring of toxicity in clinical use of acyclovir for over 50,000 patients. The safety of oral acyclovir has been examined in data from 4702 clinical trial patients exposed to acyclovir, epidemiologic and safety studies with 71,653 patients who received a least one prescription for acyclovir, and subsequently through the reporting of adverse drug events. Early in its development, acyclovir received extensive safety evaluation as it was among the first widely used nucleoside analogues, and was used cautiously. However, the rate of adverse events in clinical trials is very similar in the drug and placebo groups, with most common reports of headache and nausea in both groups. In one long-term suppression study of 1,200 people, the most frequent adverse experiences reported for acyclovir 400 mg bid were nausea (4.8%) and diarrhea (2.4%). In the same study, the most frequent adverse experiences reported in the placebo group were diarrhea (2.7%), nausea (2.4%), and headache (2.2%). Serious events, attributable to oral acyclovir in doses used for the treatment of genital herpes, have not been noted. In addition, oral acyclovir has been given in doses up to 800 mg five times a day for 21 days without serious adverse effects.  Renal insufficiency and CNS effects have been noted rarely and primarily in patients receiving high dose intravenous acyclovir, usually in the setting of co-morbid conditions.

Based on data from a pregnancy registry that followed 749 women with first trimester exposure to acyclovir, acyclovir use does not appear to result in an increased frequency or unusual distribution of birth defects as compared with the general population ;  (Acyclovir package insert). Recent trials of daily acyclovir used at the end of pregnancy to prevent abdominal deliveries, and endorsement of such approach by the American College of Obstetricians and Gynecologists, indicate the lack of safety concerns with acyclovir. The pharmacology of acyclovir supports its safety: the initial step in activation of acyclovir is phosphorylation with a virally-

encoded thymidine kinase which is present only in cells with active viral replication. Acyclovir has fewer side effects than antibiotics used in previous mass treatment studies, such as in the Rakai STD community intervention.

**Resistance.** Clinically significant resistance to acyclovir has been described in immunocompromised patients, including advanced HIV infection (CD4<100). Only a few cases of acyclovir-resistant herpes in immunocompetent persons have been described and no transmission of resistant strains has been documented . Most commonly, resistance is mediated by mutant strains that lack thymidine kinase . The frequency of such strains with in-vitro resistance, which does not necessarily imply clinically-significant resistance, has remained at <3.5% in healthy populations (>5000 patients) examined before and after introduction of acyclovir. Recent data suggest that topical, not oral, acyclovir is a risk factor for in vitro resistance. Other data suggest that intermittent rather than daily administration of acyclovir is a risk factor for development of resistance to acyclovir in immunocompromised patients. As acyclovir-resistant mutants arise spontaneously, and acyclovir decreases the amount of replicating virus, suppressive therapy may be less likely to lead to emergence of resistant strains than episodic therapy, particularly among immunocompromised persons whose lesions contain large amounts of virus, allowing proliferation of acyclovir-resistant strains. However, emergence of less sensitive strains was not seen in immunocompetent patients who received acyclovir episodically for one year, received it intermittently on weekends, or who were given suboptimal doses. Patients who received suppressive acyclovir for as long as 6 years did not have recurrent HSV-2 episodes with acyclovir-resistant strains after stopping therapy.

Sequential specimens from patients who participated in daily home culture studies on and off therapy with daily acyclovir have been tested for resistance and have indicated that breakthrough shedding was rare and not caused by resistant strains. Six (3%) of 181 isolates documented reduced susceptibility to acyclovir, but all disappeared spontaneously and were followed by recovery of sensitive viral isolates . A CDC surveillance survey in 1997-98 found <1% in vitro resistance in a total of over 1800 persons (including both HIV-infected and HIV-uninfected persons) in the 10 participating cities. Isolation of strains with reduced susceptibility (>2 mcg/ml in the plaque neutralization assay) was more common (3%) in HIV-infected patients. The significance of these in vitro findings is unclear, as these patients did not have clinically refractory herpes.

Defining clinical resistance to acyclovir remains an area of some controversy; clinical resistance varies with the immune status of the host. Thus, for highly immunosuppressed patients there are case reports of clinically refractory lesions in persons whose isolates were above 4 mcg/ml by the plaque neutralization assay. In most cases, these were HIV-positive persons and clinical resistance was seen with isolates above 10 mcg/ml. Only rare cases of clinically refractory disease have been reported in HIV-negative immunocompetent persons. The question about whether widespread prolonged acyclovir use would markedly enhance HSV-2 resistance was evaluated in a mathematical model by Blower et al. In modeling the development of acyclovir

resistance in a population treated with episodic acyclovir, Blower predicted that with wide use, acyclovir resistance may rise to up to 36% in 50 years. However, this detrimental effect was balanced by decreased HSV-2 prevalence of 74% with widespread antiviral treatment .

These data clearly indicate that the mechanism of resistance and clinical significance is different in HSV-2 infections than in HIV or bacterial infections. Specifically, risk factors such as chronic therapy that are associated with development of resistance to antibiotics or anti-HIV medications are not necessarily risk factors for development of HSV resistance to acyclovir. Widespread population-based use of acyclovir may lead to reduced susceptibility of circulating strains of HSV-2, but the critical questions are over what time period and the balance of risk to benefits. These data can be modeled hypothetically, but the question can only be answered experimentally. The first issue is whether the efficacy of the drug will result in an appropriate benefit. For resource-poor countries and perhaps even for the U.S., the "benefit" requires reduction in HIV acquisition—the purpose of this study. Whether HSV-2 resistance will emerge from breakthrough infections is something that can be evaluated subsequently in future studies. The strategy for acyclovir use for HIV prevention, if this trial is effective, is a temporary one, perhaps useful in many countries for a 5-15 year period until effective HIV vaccines and other prevention approaches become available. Hence, the risk for causing widespread HSV-2 resistance will likely be low, based on both current experimental and mathematical modeling data.

Adherence: Adherence is an issue with use of any medication. The adherence rate of twice daily acyclovir among those at risk of HIV infection is uncertain. However, all published clinical trials of acyclovir to suppress herpes shedding or ulcerations had significant efficacy, indicating a significant effect even if adherence was not perfect. In addition, preliminary findings in a study of genital HIV and HSV-2 shedding among 212 rural Zimbabwean sex workers, approximately 60% of whom were HIV-positive, found that 82% of women completed the 3 months of follow-up and missed doses (confirmed by pill count) with suppressive acyclovir 400 mg bid were only observed at 2.9% of visits.

While there is some preference for once daily dosing of medications, the amount of time without adequate antiviral levels would be even greater if a once daily medication dose is missed compared with bid medication. Even though adherence to medication in previous studies likely varied, the overall efficacy of acyclovir remained excellent. For example, in a four-month study of suppressive acyclovir, the proportion of pills taken by patients was 97% in the acyclovir recipients receiving 200 mg 5 times a day and 98% in those receiving acyclovir 200 mg bid. Furthermore, the rate of compliance did not differ in those with and without breakthrough recurrences (97% vs. 98%). Conversely, Straus et al. showed that breakthrough recurrences are not always associated with missed doses . Similarly, in a study of acyclovir 400 mg bid and asymptomatic viral shedding, breakthrough shedding occurred in 5 women, of which only one was non-adherent and took only 61% of the study pills in the preceding 2 weeks. Overall, the women took a median of 98% of the study drug

during the 5-month study. None of the published articles on the use of suppressive therapy demonstrated that non-adherence was associated with a decreased overall efficacy of acyclovir.

As with many medications, the amount of adherence required for 80% reduction in HSV-2 reactivation (the level used in the power calculations) is unknown. However, the ease of administration, excellent tolerability and lack of adverse effects likely lead to high rates of compliance, particularly for persons who are in a clinical trial in which acyclovir is being tested as a method to prevent HIV acquisition. Even though the published literature has addressed primarily the use of acyclovir in patients who had clinically evident, and sometimes severe, symptomatic genital herpes, it is encouraging to note such high rates of compliance with a twice-daily medication.

Previous studies have found that factors that can motivate adherence include patient and community-level education, and an investigator approach that includes counseling and close follow-up. Strategies to promote adherence need to be tailored differently for preventive versus therapeutic therapies. A randomized trial of several strategies to promote and monitor adherence to daily isoniazid for preventive tuberculosis (TB) therapy among injection drug users in Baltimore indicated that overall adherence was 80% and was highest among the subset randomized to supervised care, and enhanced with peer counseling. The extensive literature on TB preventive therapy and oral contraceptive pills (OCPs) summarize a number of strategies to increase adherence that will be utilized in this study, including explicit information about setting a regular time of day to take the pill, providing and monitoring knowledge about the drug, and providing explicit instructions about what to do if pills are missed.

The reasons for poor adherence can be complex, and often go beyond the doctorpatient relationship. There are 4 key aspects of treatment adherence: the patient, the social milieu, the treatment regimen, and the program support offered. Increased pill burden, complex daily dosing regimes and high side effect profiles negatively influence adherence. The literature from HIV antiretroviral therapy (ART) indicates that pill boxes, electronic devices, telephone reminders, home visits, a single cognitive-behavioral intervention and incentives all can increase adherence . In general, the more comprehensive strategies were associated with higher adherence. With respect to this study, some of the approaches used to increase adherence for ART are costly and less relevant for this multi-site international trial, which involves a simple, nontoxic, prevention strategy.

### 1.2 Rationale

Epidemiologic data consistently indicate an association between HSV-2 seropositivity and HIV acquisition among both heterosexuals and MSM. Serologically documented HSV-2 infection, regardless of history of clinically-recognized genital herpes, is a significant risk factor for HIV acquisition. HSV-2 is highly prevalent in high-risk heterosexuals in Africa (over 80% of HIV seroconverters among the monogamous Rakai HIV-discordant couples were HSV-2 seropositive) and in high-risk HIV- negative MSM in the US (30-50% HSV-2 prevalence) and Peru (50% in HIV-negative and 85% of HIV-positive MSM).

Given that genital herpes is a significant risk factor for HIV acquisition, a critical research question relates to the efficacy of daily suppressive therapy in HSV-2 seropositive individuals in reducing HIV acquisition (susceptibility) by suppressing HSV-2 reactivation in high risk HIV-negative individuals. This study is a proof-of-concept trial, designed to assess the overall efficacy of twice daily HSV-2 suppressive therapy — 400 mg of acyclovir — in preventing HIV infection among high risk, HSV-2 seropositive WSM and MSM. It will provide a simple and direct measure of the relative reduction in incident HIV infections by suppressing herpes reactivation and diminishing the enhancement of HIV susceptibility due to genital herpes.

Acyclovir is safe, highly effective, and available generically, and acyclovir resistance has not been a problem. Thus, acyclovir provides an ideal "probe" to directly test the association between HSV-2 and HIV susceptibility.

Acyclovir was selected as the optimal medication for HSV-2 suppression, based on previous efficacy studies in both HIV-positive and HIV-negative individuals. The argument has been made that a once daily regimen might be associated with higher compliance in terms of proportion of doses taken. However, the critical factor may be duration of time (or area under the curve) in which anti-virals are providing HSV-2 suppression; that interval is likely to be greater with fewer missed doses in a twice daily regimen than a once daily regimen.

Over 50 clinical trials of acyclovir therapy demonstrate 80-90% reduction in days with genital lesions, thus supporting our assumption of an overall 80% effect size in our power calculations. The dose of acyclovir 400 mg po bid was chosen as the preferred dose from both clinical and economic perspectives. Acyclovir 400 mg bid has been an effective regimen for suppression of clinical recurrences as well as asymptomatic viral shedding. This dose has been used in many studies, including several that lasted for many years (up to 10 years). While adherence to medication in these studies likely varied, the overall efficacy of acyclovir remained excellent. Other currently available regimens include famciclovir, which is also given bid, and valacyclovir, which can be given once daily. However, acyclovir is currently available generically for a fraction of the cost of valacyclovir (\$69 for a year's supply of generic acyclovir 400 mg bid). The preferred strategy is to use the medication that is most likely to be available in the participating communities after the trial. Thus, acyclovir was selected based on efficacy, cost (given that acyclovir is now available generically, and thus would be the most sustainable and cost-effective herpes medication available), minimal side effects, and an available placebo.

Previous studies in developed countries indicate high adherence with twice daily acyclovir for prevention of HSV-2 reactivation, and high efficacy even when adherence was approximately 85%. High adherence is anticipated in the sites participating in this trial through a combination of approaches that include clear

explanation about the rationale of the study (i.e., that they are being randomized to acyclovir or placebo to see if it will prevent HIV acquisition), the safety of acyclovir from many previous studies, and monthly visits in which adherence will be assessed and barriers to adherence will be addressed by the study staff. The research staff will be trained in previously-evaluated effective strategies to promote adherence, including clear and simple counseling messages related to adherence, the safety of acyclovir, and plans to manage nonadherence. Peer outreach workers have been found to be effective for recruitment, retention, and adherence assessment in some sites, such as trained MSM outreach workers in Peru, which will be used by sites to enhance adherence. Lastly, sites will attempt to assist study participants with child care and family planning needs to enhance adherence with study visits and the protocol.

This double blind, placebo-controlled intervention trial of daily antiviral HSV-2 suppressive therapy for HIV prevention has reasonable risks and benefits to the participants. First, although the observational data indicate an increased risk of HIV infection among HSV-2 seropositive persons, a reduction in HIV infection due to daily HSV-2 suppression has not yet been tested or demonstrated. Second, participants in the placebo arm will be provided more than the standard of care for many U.S. settings, by provision of episodic antiviral treatment for symptomatic herpes outbreaks.

In summary, the HPTN provides a unique opportunity to assess the effect of HSV-2 suppression on reducing HIV acquisition among MSM and WSM populations who have the highest HSV-2 seroprevalence and HIV incidence rates globally. This proof-of-concept trial is designed to assess the overall efficacy of twice daily HSV-2 suppressive therapy — 400 mg of acyclovir — in preventing HIV infection among high risk, HSV-2 seropositive heterosexual women and MSM. This study will provide a simple and direct measure of the relative reduction in incident HIV infections by suppressing HSV-2 reactivation, thus diminishing the enhancement of HIV susceptibility caused by genital herpes. Preventive and therapeutic candidate HSV-2 vaccines are being developed and, in the future, a highly efficacious HSV-2 vaccine could supplant acyclovir. Lastly, even if ART therapy reduces HIV transmission among HIV-discordant couples and proves to have higher efficacy than acyclovir, our study findings will be valuable in two ways:

- 1) The mechanism of acyclovir's effect differs and would likely be complementary to the effects of ART.
- 2) The populations that can benefit from acyclovir are much larger than those that will be utilizing ART therapy, based on HSV-2 seroprevalence relative to the proportion of HIV+ with CD4<200 or symptomatic AIDS who would be eligible for ART in developing countries as it becomes available.

Procurement of study drug has been supported in part by a contribution from Glaxo SmithKline.

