## 2.3 Study Design

This is a phase III, multi-site, randomized, double-blind, placebo-controlled trial. Between 2820 and 3012 high-risk, HIV-negative, HSV-2 seropositive WSM and MSM will be enrolled. Women who have sex with men (WSM) will be enrolled at study sites in Lusaka, Zambia, Harare, Zimbabwe, and Johannesburg, South Africa. Men who have sex with men (MSM) will be enrolled at study sites in Lima, Iquitos, and Pucallpa, Peru; Seattle, WA, USA; New York City; NY, USA; and San Francisco, CA, USA.

Due to slow enrollment at the time of the printing of this version of the protocol, participant follow-up is increased from 12 months to 18 months. Newly enrolled participants will be followed for 18 months after enrollment. In addition, the Protocol Team will evaluate the benefit and feasibility of extending follow-up for currently enrolled participants at each site (extending from 12 to 18 months). Following this evaluation, the re-consent process will be further examined in the first month of implementation at each site involved in the process. The protocol team will then determine whether a particular site will continue re-consenting participants at that site. The sample size for the study will ultimately be determined by the proportion of currently enrolled participants who will be followed for 12 vs 18 months.

HSV-2 serostatus will be determined from samples taken at screening by Focus Technologies™ (formerly MRL) HSV-2 EIA. Participants with a low positive index between and including 0.9 and 3.4 according to the Focus serology, but are HSV-2 positive by the University of Washington's HSV-2 Western blot test, will also be eligble. HIV serostatus will be determined according to the algorithms presented in Appendices II and III. Confirmatory second samples will only be drawn in case of discordant test results on the first sample or if mandated by local law.

Pre-test, risk reduction, and post-test counseling will be provided to all participants; HSV-2 counseling will include information on the natural history of HSV-2, clinical

manifestations, recognition of prodromal symptoms and lesions, risk of transmission during subclinical reactivation as well as symptomatic herpetic lesions, and the epidemiologic and clinical data about HSV-2 and HIV interactions.

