### 3 STUDY POPULATION

Between 2820 and 3012 high risk HIV-negative, HSV-2 positive WSM and MSM will be selected for the study according to the criteria in Section 3.1, 3.2, and the guidelines in Section 3.4. They will be recruited as described in Section 3.3 and randomized to study drug as described in Section 7.4. Conditions for withdrawal from the study are described in Section 3.6.

The following study sites will participate in this trial, of which three sites will recruit high-risk WSM and four sites will recruit high-risk MSM.

- Harare, Zimbabwe
- Lusaka, Zambia
- Lima, Iquitos, and Pucallpa, Peru
- Seattle, WA, USA
- New York, NY, USA
- San Francisco, CA, USA
- Johannesburg, South Africa

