#### 7.6.2 Secondary Analyses

The primary analysis of the treatment effect will be pooled over the two risk groups: MSM and heterosexual women. As a secondary analysis, separate Cox regressions will be used to estimate the relative risk and confidence interval for a treatment effect in the heterosexual women and MSM subgroups.

Adherence will be measured monthly. The analysis of adherence will be structured to allow us to estimate the adherence rate, test for a difference in compliance between the placebo and treatment groups, test for a trend over time in the compliance rate and examine the relationship between adherence and markers of risky sexual behavior. Specifically, a logistic regression with proportion of tablets taken each month as the outcome and treatment group, clustering of missed doses, time on study and markers of risky sexual behavior as predictors, will be used. Since the analysis will involve repeated observations on individuals, robust variance estimates , will be used to evaluate statistical significance and compute confidence intervals. Standard methods for model checking will be used to check the assumption of a linear trend over time in compliance.

The relationship between compliance and risk of incident HIV infection will also be examined. A proportional hazards model with HIV infection as the endpoint and self-reported adherence, subgroup (women versus MSM) and their interaction as covariates (time-dependent in the case of adherence) will be fit to the data from those individuals randomized to acyclovir. If the adherence is related to risky sexual behavior then the relationship between adherence and risk of HIV infection may be found to differ between MSM (where risk of HIV infection is also related to risky sexual behavior) and women (where risk of HIV infection is likely to be less related to the woman's sexual behavior and more related to her partner's behavior).

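### The monthly adherence regression has no site or risk-group term, so its association between adherence and sexual-risk behaviour is open to confounding by site

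*Supplement*

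**What the plan says.** Section 7.6.2 gives several purposes for the adherence analysis. One is to "examine the relationship between adherence and markers of risky sexual behavior". The model is then spelled out: the outcome is the proportion of tablets taken each month, with "treatment group, clustering of missed doses, time on study and markers of risky sexual behavior as predictors, will be used". Neither site nor risk group is in the list, and no stratified version is given. On variance the section says: "Since the analysis will involve repeated observations on individuals, robust variance estimates" will be used. The separate HIV-risk model in the same section, fitted in the acyclovir arm, does carry "self-reported adherence, subgroup (women versus MSM) and their interaction as covariates".

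Site and risk group are tied together by design. Section 2.3 states: "Women who have sex with men (WSM) will be enrolled at study sites in Lusaka, Zambia, Harare, Zimbabwe, and Johannesburg, South Africa". It places all MSM in Peru and three US cities. Section 3 says that "three sites will recruit high-risk WSM and four sites will recruit high-risk MSM". Section 3.1 requires women to report unprotected vaginal sex, while men need only report anal intercourse, with no condition on condom use. Section 3.2 has a monogamy exclusion for MSM only.

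On adherence, Section 1.1 counts social setting and programme support among four things that shape it. Section 1.2 says peer outreach workers have helped with enrolment, with retention and with "adherence assessment in some sites, such as trained MSM outreach workers in Peru, which will be used by sites to enhance adherence". Section 7.4 stratifies randomisation by site.

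**The concern.** The association between adherence and risk behaviour is not a randomised comparison, so site-stratified randomisation does not protect it. If sites differ both in average adherence and in how common the risk markers are, a pooled regression without site turns those two differences into an association between marker and adherence, even when none exists at any site. Robust variance corrects the standard errors for repeated monthly records. It does not remove confounding.

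The marker distributions can be expected to differ, because the sites enrol different sexes under different behavioural criteria. Adherence may well differ by setting. A site artefact could then be reported as a behavioural finding. It could also colour the discussion of adherence and HIV risk in women and MSM, which opens with the possibility that adherence is related to risky behaviour.

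**Working it through.** **The plan's own figures.** The documents give no figure for the adherence model. The design figure, needed below, reproduces. With r = 0.51, two-sided α = 0.05 and 90% power (Section 7.3), L = {(1.960 + 1.282)/(0.5 × ln 0.51)}² = 92.7, rounded up to 93, as stated.

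**Inputs from the protocol.** N = 2,820 (lower end of the target), three WSM and four MSM sites, risk groups of similar size, two tablets a day, and robust variance clustered on the person.

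**Assumed inputs.** Adherence and marker prevalence at each site; one binary marker R that is unrelated to adherence within site; six months of 60 doses; no effect of arm on adherence. For person i at site s, logit pᵢ = logit aₛ + bᵢ, with bᵢ ~ N(0, 0.8²) and R ~ Bernoulli(rₛ). Clustering is taken as the share of missed doses that fall on days when both doses were missed.

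**Models.** Logistic regression of the monthly proportion on R, arm and month; then with clustering added (the planned four predictors); with a risk-group term and no clustering; and with site terms, without and with clustering. There were 60 runs per scenario. The true within-site odds ratio is 1.00 throughout. Cells show the odds ratio for R and the share of runs with p<0.05.

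| Scenario: adherence aₛ; marker rₛ | No site term | Planned four predictors | Risk-group term | Site terms | Site terms and clustering |
|---|---|---|---|---|---|
| A: 85% everywhere; 30% WSM, 60% MSM | 0.995, 3% | 0.996, 2% | 0.994, 2% | 0.994, 2% | 0.995, 2% |
| B: 82% WSM, 88% MSM; 30%, 60% | 1.145, 100% | 1.085, 98% | 1.002, 8% | 1.003, 8% | 1.003, 7% |
| C: one MSM site 92%, others 85%; 60%, others 40% | 1.052, 35% | 1.033, 32% | 1.044, 33% | 1.000, 2% | 1.000, 5% |
| D: 75% WSM, 90% MSM; 30%, 70% | 1.466, 100% | 1.220, 100% | 0.996, 7% | 0.996, 7% | 0.999, 5% |
| E: 84% WSM, 86% MSM; 45%, 55% | 1.019, 7% | 1.012, 10% | 1.005, 5% | 1.005, 5% | 1.003, 5% |
| F: 75% WSM, 90% MSM; 50% everywhere | 1.003, 3% | 1.002, 3% | 1.004, 7% | 1.004, 7% | 1.002, 3% |

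With 60 runs, the simulation standard error around 5% is √(0.05 × 0.95/60) = 2.8 percentage points. Rates up to about 10% are therefore not distinguishable from nominal.

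**Hand check of the mechanism, ignoring person-level spread.**
- Scenario B: marker-positive people are 0.3/(0.3 + 0.6) = 1/3 WSM, so their mean adherence is 82/3 + 88 × 2/3 = 86.0%. Marker-negative people are 0.7/(0.7 + 0.4) = 0.636 WSM, giving 84.2%. The odds ratio is (0.860/0.140)/(0.842/0.158) ≈ 1.15.
- Scenario D: 0.3 × 75 + 0.7 × 90 = 85.5% against 0.7 × 75 + 0.3 × 90 = 79.5%. The odds ratio is (0.855/0.145)/(0.795/0.205) ≈ 1.52, close to the simulated 1.47.

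**Direction.** All scenarios above pair higher adherence with higher marker prevalence, so the bias is upward. In a further simulation (2,900 participants: half African WSM, a quarter Peru MSM, a quarter US MSM; 14 months), marker prevalence was 20/50/70%. Adherence of 95/90/85% gave an odds ratio of about 0.64, and 85/90/95% gave 1.47. Neither figure is known to include the clustering covariate, so they illustrate direction only.

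**Events for the HIV-risk model.** Expected infections in the acyclovir arm are 93 × 0.51/1.51 = 31.4, or about 4.5 per site over seven sites.

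**The case against.** The strongest case against is that the evidence for differing sites is thin. A reader might infer from Section 1.2 that adherence support does differ by site. The sentence does not establish this: it cites Peru as an example and says outreach workers will be used by sites, without saying which. Section 5 promises instructions to standardise procedures across sites. That objection stands, so confounding is a risk and not a demonstrated fact.

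The sizes rest on assumed gradients. The planned clustering covariate shrinks them (1.15 to 1.09, and 1.47 to 1.22), and small gradients do little. This also stands. It limits what can be said about size, but not the existence of the gap.

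A pooled descriptive association is a legitimate target, and the plan never says it wants a within-person or causal relation. True, but a pooled figure that cannot be told apart from site composition says little about behaviour.

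Adjustment covariates are often left to an analysis plan, and none is shown. Here, however, the protocol names the predictors itself, and an analysis plan that followed it would carry the omission over.

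A reader might also infer that the HIV-risk model depends on this regression, or should itself be stratified by site. No coefficient passes from one to the other. The women/MSM interaction is fitted whatever the adherence regression shows. With about 31 expected infections, site stratification there is a trade-off that has not been assessed.

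**Conclusion.** The point holds as a vulnerability in one secondary, non-randomised analysis. As specified, the association between adherence and risk behaviour could be partly or wholly produced by differences between sites. The bias requires both adherence and the marker to vary by site; it vanishes when either is constant (scenarios A and F). A risk-group term alone is not enough when the difference lies between sites within a risk group: scenario C keeps 33% false positives with it, against 2% with site terms.

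The documents do not support saying that the association is confounded, how large the bias is, or which way it runs. Nor do they support extending the point to other results. Site-stratified randomisation protects the acyclovir versus placebo adherence comparison from site confounding, and the primary Cox analysis does not use this model.

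**What to change.** In Section 7.6.2, add site (the randomisation stratum) as a fixed effect in the monthly adherence regression, and report the association between adherence and risk behaviour as a within-site estimate. Because sites are nested in risk group, site terms also absorb the women/MSM difference in average adherence. A marker-by-risk-group interaction is a reasonable option if the association is expected to differ between women and MSM.

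The cost is one parameter fewer than the number of sites (six for seven sites), against 2,820 to 3,012 participants with monthly records. Site is already recorded and no new data are needed. If the sites prove alike, little is lost. The result remains observational: site terms do not remove confounding between individuals within a site.

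Leave the adherence and HIV-risk proportional hazards model as specified. Stratifying it by site should be at most a sensitivity analysis.
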